#### Rationale for Sampling Plan

A final sample size of 32 per group (after accounting for  $\sim$ 10% attrition) provides sufficient power (80%) to detect a medium effect size (d = 0.71) based on pilot findings, particularly in measures like fractal scaling.

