## D. Criteria for Participant Selection

#### Target Recruitment:

- 32 individuals with BD (BD-I or BD-II, currently in a depressive or mixed state)
- 32 healthy control participants

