## **Participant Discontinuation and Withdrawal**

Participants will be informed that participation is completely voluntary and that they may withdraw from the study at any time. If a participant withdraws or is discontinued, the reason and the method used to determine the need for discontinuation will be documented. Participants will be withdrawn if they revoke consent or if the investigator determines that continued participation is not in their best interest. This may include newly emerging or worsening suicidal ideation. Participants may also be withdrawn if they do not comply with staff instructions or are unable to remain still in the MRI scanner and continue to exhibit frequent motion despite guidance, as excessive motion renders the MRI data unusable. In the event of a system failure that prevents completion of the scanning session, we will attempt to reschedule the session within one week of the canceled appointment. If the participant is unavailable during this time, they will be withdrawn from the study.

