#### Lost to Follow-up

A participant will be considered lost to follow-up if they fail to return for a scheduled 2nd visit and study staff are unable to contact the participant after 3 attempts.

The following actions must be taken if a participant fails to return for a 2nd session:

- The study staff will attempt to contact the participant, ascertain if the participant wishes to and/or should continue in the study, and as needed, reschedule the missed visit.
- Before a participant is deemed lost to follow-up, the study staff will make every effort to regain contact
  with the participant (where possible, 3 telephone calls, 3 text messages, or, if necessary, an email or
  certified letter to the participant's last known mailing address or local equivalent methods). These
  contact attempts will be documented in the participant's research record or study file.
- If there is any concern about the safety of a participant lost to follow-up (e.g., due to previously recorded suicidal ideation) and study staff are unable to reach the individual, then confidentiality may be broken and the COPES [contact]) may be called to help ensure safety of the participant.
- Should the participant continue to be unreachable, he or she will be considered to have withdrawn from the study with a primary reason of lost to follow-up.

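### The protocol uses 32 per group both as the number to recruit and as the number left after about 10% attrition; if 32 are recruited and none replaced, power at d = 0.71 is about 76–77%, not 80%

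*Protocol*

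**What the plan says.** Section D of the protocol gives the sample size in two places.

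- **Target Recruitment** lists "32 individuals with BD (BD-I or BD-II, currently in a depressive or mixed state") and "32 healthy control participants".
- **Rationale for Sampling Plan** refers to "A final sample size of 32 per group (after accounting for" roughly 10% attrition), and states that this number "provides sufficient power (80%) to detect a medium effect size (d = 0.71) based on pilot findings".

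Section F provides for participants to leave after consent. Under Participant Discontinuation and Withdrawal they may be withdrawn for persistent movement in the scanner, "as excessive motion renders the MRI data unusable". Under Lost to Follow-up, "A participant will be considered lost to follow-up if they fail to return for a scheduled 2nd visit" and staff cannot reach them. Neither subsection says that such participants are replaced, and no enrolment figure above 32 per group appears anywhere in the protocol.

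**The concern.** One number does two jobs. A recruitment target counts people entering the study; a final sample after attrition counts those who remain. With losses of about 10%, the two cannot be equal unless each lost participant is replaced, and the protocol does not say that this will happen.

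Two things are at stake. The first is operational: the text does not settle whether recruitment stops at 64 enrolled, leaving about 58 to analyse, or continues until 64 are analysable. The second is the power claim. It is the only one in the protocol, and it is correct for one of these meanings but not for the other.

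**Working it through.** **Inputs from Section D:** d = 0.71; power 80%; attrition about 10%; two equal groups; 32 per group.

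**Assumption:** a two-sided comparison of two independent means at alpha 0.05. The protocol states no test, alpha or sidedness.

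**Step 1. Reproduce the stated figure.** With n analysed per group, the noncentrality is d × √(n/2). The normal approximation to power is Φ(d√(n/2) − 1.96). The t-test version uses the noncentral t distribution with 2n − 2 degrees of freedom.

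For n = 32: 0.71 × √16 = 2.84, and Φ(2.84 − 1.96) = Φ(0.88) = 81.1%. The noncentral t gives 79.8%. Solved for sample size, 80% power needs 31.1 per group (normal) or 32.1 (t). The stated 80% is therefore reproduced at 32 *analysed* per group.

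**Step 2. Apply attrition to 32 recruited.** 32 × 0.9 = 28.8, about 29 per group. For n = 29: 0.71 × √14.5 = 2.704, and Φ(2.704 − 1.96) = Φ(0.744) = 77.1%. The noncentral t gives 75.7%.

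**Step 3. Vary the attrition,** since the protocol gives it only approximately. The 5% and 15% rows are assumed values.

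| Attrition from 32 | Analysed per group | Power (t-test) |
|---|---|---|
| none | 32 | 79.8% |
| 5% | 30 | 77.2% |
| 10% | 29 | 75.7% |
| 15% | 27 | 72.6% |

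**Step 4. Effect detectable with 80% power.** The normal approximation is (1.96 + 0.84) × √(2/n). At n = 29 it gives 0.74; the t-test gives 0.75. At n = 32 the t-test gives 0.71, the protocol's own value.

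**Step 5. Could a one-sided test reconcile the text?** A one-sided t-test at 0.05 gives 87.8% at n = 32 and 84.8% at n = 29. It needs 25.2, so 26, analysed per group for 80% power; 26/0.9 = 28.9, so 29 recruited. It arrives at 80% with neither 32 recruited nor 32 analysed.

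**Step 6. Recruits needed to keep 32.** 32/0.9 = 35.6, so 36 per group, or 72 in total instead of 64.

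**The case against.** The strongest reply is that no calculation in the protocol is wrong. The sampling rationale is the more specific text: it calls 32 the final number, says attrition has been allowed for, and its 80% reproduces at 32 analysed. The recruitment list is two lines under a heading that could be read loosely as the intended group sizes. Replacement is not prescribed, but it is not forbidden either. On that reading the power stands and only a label is loose. Moreover, a difference of about four points, with d taken from pilot data and attrition only approximate, would not change how a cross-sectional imaging study is interpreted.

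Much of this stands. The figures do favour 32 as the number analysed, and the lower power follows only if recruitment stops at 32 and losses are not replaced. The withdrawal and follow-up subsections show that losses are expected; they do not rule out replacement. The size is modest.

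The conflict remains all the same. Even on the favourable reading, the heading presents a completer count as a recruitment target, and the number needed to reach it appears nowhere. The rationale says attrition has been allowed for, yet the only recruitment figure equals the figure after attrition. That mismatch does not depend on any assumption about alpha or the test.

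**Conclusion.** The concern holds. The two statements in Section D are incompatible unless lost participants are replaced, and the protocol does not provide for that.

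- **If 32 is the number analysed,** the 80% is right, the recruitment target is mislabelled, and the number to recruit is missing.
- **If 32 is the number recruited,** about 29 per group are analysed. Power at d = 0.71 is then about 76% (t-test) to 77% (normal approximation), some four points below the corresponding value at 32, and 80% power applies to d of about 0.75.

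The power figures rest on an assumed two-sided 0.05 test, which is supported by its reproducing the protocol's own 80%, and on attrition of 10% without replacement. The point should be fixed, but it does not threaten the study.

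**What to change.** The sponsor should decide which number 32 is, make the two parts of Section D agree, and state the test and alpha behind the power figure.

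- **If 32 is recruited,** restate the rationale along these lines: *We will recruit 32 per group. With about 10% attrition, about 29 per group will be analysed, giving about 76% power for d = 0.71, or 80% for d = 0.75, with a two-sided t-test at alpha 0.05 (test and alpha to be confirmed).* The cost is one sentence and a slightly less favourable power figure.
- **If 32 is analysed,** relabel the target as completers with usable data, and add either the number to recruit (about 36 per group) or a rule that lost participants are replaced until 32 per group are analysable. At 36 per group this means (36 − 32) × 2 = 8 more participants. Using the compensation table in Section K, that is at most 8 × $190 = $1,520 in payments and up to 8 × 2 = 16 scanner hours.

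Either route resolves the conflict. Recruiting more is not required if the sponsor accepts the lower power and says so.

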#### E. Recruitment and Retention Plans

## Recruitment Strategy

Participants will be recruited through:

• The NeuroMAP Recruitment and Assessment Core at LIBR (WCG IRB# 20231660)

During NeuroMAP Core study procedures, initial eligibility screening will occur via phone. Individuals who meet preliminary criteria will be invited for an in-person screening session, where they will undergo a structured psychiatric assessment using the MINI interview and standardized self-report measures. No identifying information will be collected prior to voluntary contact with LIBR research staff. Once NeuroMAP Core data collection is complete, study staff will screen subjects against the eligibility criteria listed above. Trained study staff will contact individuals who are determined to be initially eligible to confirm eligibility and interest in discussing the informed consent.

#### Retention and Compensation

Participants will complete two sessions: (1) Preparation visit and (2) MRI scan visit. Participants will be compensated \$20 per hour for time spent completing written and oral tests, and \$50 per hour for time spent in the scanner (scanning time will not exceed 2 hours). The detailed payment structure is described in Section L. Compensation for Participation. Retention is further supported by flexible scheduling, reminder calls/emails, and a structured and respectful participant experience.

### F. Study Procedures and Protocol

## Study Site

Participants will complete the study procedures at the Laureate Institute for Brain Research (LIBR) in Tulsa, OK. All data will be collected by LIBR staff trained on the study protocol and in research and good clinical practices. Data will be stored electronically using REDCap on LIBR networks and IT security.

#### Overview of Study Design

This is a cross-sectional, neuroimaging-based study designed to assess emotional state dynamics in individuals with bipolar disorder (BD) and healthy controls (HC) using:

## LIBR #2025-005

## 10/9/2025

- fMRI-based Think and Regulate Affectivate states Task (TReAT)
- Resting-state fMRI
- Structural MRI and white matter tractography
- Self-report questionnaires
- Computational metrics (e.g., metastability, fractal scaling, network controllability)

## Session Timeline

The study sessions consist of two visits: one preparation session and one MRI scanning session. Table 1 describes the overall outline of this study and measures obtained at different points in time.

Table 1. Experimental procedure and Assessments

		Visit1		Visit 2		
Content	Procedures/Assessments		1-7 days after Visit 1			
			Before MRI	During MRI	After MRI	
Informed Consent		Χ				
Mania	Young Mania Rating Scale (YMRS)		X			
Depression	Montgomery–Åsberg Depression Rating Scale (MADRS)		X			
Trait Rumination	Ruminative Response Scale (RRS) [15]	Х				
State Rumination	Brief State Rumination Inventory (BSRI)	Х	X			
Hedonic	Temporal Experience of Pleasure Scale (TEPS)	Х				
Emotion Regulation	Emotion Regulation Questionnaire (ERQ)	Х				
Emotion Regulation	Difficulties in Emotion Regulation Scale (DERS)	Х				
Positive/	Positive and Negative Affect Schedule-	Х	X		X	
Negative Valence	X (PANAS-X)					
Depression	16-item Quick Inventory of Depressive Symptomatology (QIDS)	Х	X			
Social Functioning	Sheehan Disability Scale (SDS)	Х				
Trait-anxiety	State Trait Anxiety Inventory (STAI-T)	Х				
State-anxiety	State Trait Anxiety Inventory (STAI-S)		Х		Х	
Depression	PROMIS Depression	X				
Anxiety	PROMIS Anxiety	Х				
Hedonia	PROMIS General Self-Efficacy Scale	Х				
Anger	PROMIS Anger	X				

Hedonia	PROMIS Positive Affect and Wellbeing	Х			
Subjective cognitive abilities	PROMIS Applied Cognition-Abilities	Х			
Subjective cognitive concerns	PROMIS Applied Cognition-General Concerns	X			
Physical function	PROMIS Fatigue	X			
Sleep	PROMIS Sleep Impairment and Disturbance	Х			
Thought collection wor	k sheet (study original)	X			
Emotion Intencity of events	Likert scale for positive or negative emotions	х	X		
MRI screening	MRI safety-screening questionnaire		Χ		
Alcohol and drug	Breathalyzer and urine drug screening test		X		
Pregnancy (only for female)	Urine-screening pregnancy test		Х		
Emotional State	Affective slider (emotional valence and arousal)			X	
Fatigue	Likert scale (study original)			Χ	
Comfort during the session	Feedback Questionnaire † (study original)				Х
Physiological measurement (Cardiogram, Respiration)				Χ	

<sup>†The Feedback Questionnaire assesses the participant's overall comfort during the session. It includes the following items: 1) How pleasant was the current MRI session for you? 2) How unpleasant was the current MRI session for you? 4) How successful do you feel you were in following the instructions and tasks? 5) How did you feel about the amount of time you spent in the scanner?

## **Preparation Session**

#### **Informed Consent Process**

Informed consent will be obtained by a member of the research team who has received training specific to this study. All participant interactions will take place in private interview or exam rooms, or via private virtual meetings. The consent review process may be conducted either in person or virtually.

Documented informed consent will be obtained once the consent form has been reviewed and the individual agrees to participate using the IRB-approved informed consent document. Participants will be provided with a copy of the signed consent prior to conducting study related activity. All volunteers will be at least 18 years old and will be asked to give fully informed, documented consent, following procedures already approved by the IRB. Care will be taken to explain the study thoroughly, and the process will be documented with signatures from both the participant and the individual obtaining consent.

## **Protection Against Coercion**

The researcher will remind participants that participation is strictly voluntary and that they have the right to withdraw at any time without penalty. Family members may be present during the consenting process and may assist in discussing the study with the participant, if requested.

#### **Participant Capacity**

All individuals enrolled in this study will have the capacity to consent. As noted previously, individuals with moderate to severe neurocognitive disorders will be excluded from the study.

#### Participant/Representative Comprehension

During the written informed consent process, the participant's understanding of the study protocol will be assessed and documented by trained study staff. If a participant is unable to demonstrate adequate understanding of the protocol, they will not be enrolled in the study.

## Self-Report Measures

After the informed consent document is signed during Visit 1, the study participants will be asked to complete a series of questionnaires either in-person using a LIBR iPad or computer, or remotely using a link sent to the participant's email. Data collected from these questionnaires will be used to characterize the study population and examine how individual differences relate to brain activation metrics.

Participants will be asked to complete several questionnaires related to mood, clinical symptoms, traits and personality characteristics, daily life functioning, and medical and mental health history. These self-report questionnaires are listed in Table 1. Self-report measures may be completed at home using a link from REDCap, as needed.

Participants will recall eight autobiographical events, each clearly associated with one of two thinking patterns: rumination (past negative events) or reminiscence (past positive events), which will be used in the MRI task. They will generate four events per category and write brief, keyword-based descriptions to assist with memory recall inside the MRI scanner. Details of each event will not be requested, allowing participants to provide personal events honestly.

#### **MRI Scanning Visit**

Participants will be scheduled for Visit 2 one to seven days after Visit 1 is complete. The following instruments and scans will be conducted during the MR scanning visit.

#### Pre-scan Assessments and MRI Preparation

Prior to scanning, participants will receive task instructions and complete a brief training session (15–30 minutes) to ensure understanding. They will rate distress levels related to autobiographical memories used in the task via a Lickert Scale. Participants will also be instructed on enhancing positive emotion during the regulation block using brief strategies adapted from Amplification of Positivity (AMP) psychotherapy [12, 16]. MRI eligibility will be confirmed before study entry. On the day of the scan, participants will complete the standard MRI Environment Screening Form. Alcohol and drug use will be screened using a breathalyzer and urine drug screening kit. Female participants will also undergo a urine pregnancy test. Vision correction will be provided if needed.

All standard MRI safety and comfort measures will be implemented: removal of ferromagnetic items, communication setup, ear protection, and physical stabilization (e.g., neck pillow, knee support). Participants will be positioned in the scanner, fitted with physiological monitoring devices (pulse oximeter and respiration belt), and given an emergency squeeze ball. The scan operator will ensure comfort, verify task screen visibility, and initiate communication before starting the scan.

LIBR #2025-005

10/9/2025

## MR Safety Screening

An MR Environment Screening questionnaire will be completed by each participant. The MRI safety-screening questionnaire is developed and distributed by the Institute for Magnetic Resonance Safety, Education, and Research (IMRSER) in Los Angeles, CA\*. The safety-screening questionnaire probes for possible occupational exposure to metal slivers or shavings (remnants of which may remain lodged in a participant's head or neck), surgical clips or shrapnel, cochlear implants, or any other form of ferrous metal implanted in or on the participant's body. Participants answering in the affirmative to any of these conditions will be excluded. All subjects with any form of implanted wires, metal, or electronic devices will be excluded. All persons involved in this protocol will receive MR safety training conducted at the LIBR.

\*INSTITUTE FOR MAGNETIC RESONANCE SAFETY, EDUCATION, AND RESEARCH [name], http://www.imrser.org

Although there are no known risks of MR to pregnant women, there may be unknown risks. Therefore, females who are pregnant will not participate in this study. To ensure that female subjects are not pregnant at the time of the MRI procedure, all female participants will undergo a standard urine-screening pregnancy test prior to participation in any MRI scanning.

## Physiological Monitoring

Physiological signals will be acquired through physiological monitoring of pulse rate using a finger-tip pulse oximeter throughout the MRI session [17]. A respiration belt that fits comfortably between the participant's chest and waist to measure respiratory changes. The concurrent information on pulse rate will be used to remove physiological fluctuations from the fMRI data.

## MRI scanning

The MRI scan session includes a structural brain scan (T1-weighted image), field map scans (phase-encoding direction-flipped images with echo-planar imaging [EPI]), functional scans (T2\*-weighted images using EPI to acquire blood-oxygenation-level-dependent [BOLD] functional MRI time-series data), and diffusion-weighted imaging (for diffusion tensor imaging [DTI] and white matter tractography). Figure 1 (upper panel) illustrates the sequence of scans. The total scan time is expected to be under 2 hours.

Functional MRI scans include both resting-state scans and scans acquired during the Think and Regulate Affective states Task (TReAT). The resting-state scan is 12 minutes and participants are instructed to stay still while fixating a cross sign displayed on the screen. Participants' motion will be monitored in real time during the MRI scan. If frequent significant motion is observed, the scan will be paused, the participant will be reminded of the importance of remaining still, and the scan will be restarted from that session.

[figure not shown]

Figure 1

## Think and Regulate Affective states Task (TReAT)

Figure 1 (lower panel) illustrates the sequence of the Think and Regulate Affective states Task (TReAT). TReAT consists of seven types of blocks. In the **Think** block, a short description (keywords) of an autobiographical event is presented, and participants engage in self-relevant emotional thoughts for 20 seconds. These keywords are provided by the participants using a thought collection worksheet (study-specific) during Visit 1. The Think block is followed by a **Rating** block, during which participants use the Affective Slider [18] to rate valence and arousal based on the preceding Think block while viewing the same keywords. Eight seconds (four per measure) are provided for responses. In the **Regulation** block, participants are instructed to amplify positive mood for 20 seconds while continuing to view the same keywords. At the end of this block, another **Rating** block is presented for eight seconds to assess the affective state during the Regulation block. In the **Attention** block, an array of five arrows is presented, and participants must respond to the direction of the center arrow within two seconds per trial; each block contains six trials. In the Rest block (**Rest**), a fixation cross is displayed for 16 seconds, during which participants are instructed to clear their minds and avoid directed thoughts. A **Rating** block follows the Rest block to assess the affective state during resting. These blocks will be repeated eight times in one fMRI scan run, and four runs will be performed.

#### Post-Scan Assessments

At the end of each scanning run, participants are asked to evaluate their task performance, level of sleepiness, and fatigue using a Lickert scale in response to the following questions: 1) How difficult was it to engage with your thoughts during the thinking blocks? 2) How successful were you in engaging with your thoughts during

the thinking blocks? 3) How sleepy were you during the scan? 4) How emotionally drained do you feel right now? 5) How tired are you right now?

After the scanning session, participants complete the PANAS-X and STAI-S to assess their current emotional states. In addition, the Feedback Questionnaire is administered to evaluate the participant's overall comfort during the session (see Table 1).

